1.1. Study design

The Multi-Arm Parallel-Group Exploratory Trial (NCT04355663) was realized between May 2015 and May 2017. MS patients were divided into three groups by an independent study coordinator according to availability of each therapist (in Groups 1 and 2) and amount of FES devices to borrow (in Group 3), and underwent three kinds of PT. At baseline and after the end of the two months' therapeutic program, white matter integrity was estimated from DTI and a blinded assessor evaluated clinical outcomes.

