1.2. Participants

Patients with defined MS (13) were recruited from the MS Centers of Hospitals in the Czech Republic in accordance with the following inclusion criteria: prevailed spastic paraparesis, stable clinical status and treatment in the preceding 3 months determined by neurologist, Expanded Disability Status Scale score (EDSS) ≤ 7.5 (14). The study was powered in order to provide 80% power for weak to moderate effect size (Cohen's $d=0.2-0.5$). 120 people were initially assessed for eligibility, 92 were allocated into three groups; from these 71 participants finished their therapeutic programs. Data of ten patients were discarded upon the visual control, due to the low quality of DTI acquisition resulting in 61 participants entering the central analysis. This sample provides 80% power to detect at $p<0.05$ effects of minimal size $d=0.36$ (weak to moderate effect size). For distribution of participants into groups during the study see Figure 1, for their baseline characteristics see Table 1. All subjects signed an informed

consent form approved by the Ethics Committee of Kralovske Vinohrady University Hospital in Prague (full trial protocol EK-VP/22/0/2014 is available there).

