1.3. Interventions

All groups underwent two months' ambulatory neuroproprioceptive PT led by well-educated (MSc.), experienced (at least two years' practice with pwMS) therapists specially trained in each method. Treatments were individually designed according to patient status. The therapists offered their full help and adopted the schedule, so each patient was able to complete the whole program. To increase adherence, therapists provided effective reminders and established confidential relationships.

Group 1 underwent 16 face-to-face sessions (1 hour, twice a week for two months) of MPAT (10), method developed and verified by our team. In this therapy, patients are corrected into a postural position where the joints are functionally centered. Afferent stimuli are then applied to activate motor programs in the brain, which then lead to the co-contraction of the patient's whole body when lying, sitting, standing up or moving forward. Activated programs are repeated under various conditions and in different situations and environments to teach the patients to automatically use the acquired motor skills in daily life. Therapy was realized at Faculty Hospital Royal Vineyard.

Group 2 underwent 16 face-to-face sessions (1 hour, twice a week for two months) of VRL (15), which is a standard approach for patients with MS in the Czech Republic. During the therapy, global patterns of the reflex locomotion are activated by stimulation of specific zones, with the individual placed in a precisely determined initial position (supine, prone and side laying, low kneeling position). These movement patterns have the qualities of the forward movement (locomotion) and the

movement responses are precisely defined. Reflex locomotion (reflex turning and reflex creeping) is used in therapy to activate involuntarily responses of muscle function, which are necessary for spontaneous movements. Therapy was realized at Motol University Hospital.

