1.4. Clinical outcomes

Demographic and anamnestic data were collected by a neurologist, namely gender, age, length of disease, type of MS (relapsing-remitting, primary or secondary progressive) and EDSS.

The balance [Berg Balance Scale, BBS (17) and Timed up and go – TUG (18)] was examined and *patient-reported outcomes* [the 12-item Multiple Sclerosis Walking Scale, MSWS-12 (19) and MS impact with the 29-item Multiple Sclerosis Impact Scale, MSIS-29 (20)] were collected.

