1.5. White matter integrity

All participants underwent magnetic resonance imaging on a 3T magnetic resonance scanner (Siemens Trio Tim, Erlangen, Germany) using a 12-channel phased-array head coil. The acquisition protocol consisted of T1-weighted and T2-weighted

anatomical scans, and diffusion weighted imaging using spin echo epi sequence with following parameters TR=9100 ms, TE=96 ms, FOV=260x211 mm, 64 contiguous axial slices with 2 mm thickness, b=0 and 1100 s/mm², 64 gradient directions.

For the DTI pre-processing, a combination of FSL tools (FMRIB Software Library, <http://www.fmrib.ox.ac.uk/fslwiki>, version 5.0) and MRtrix3 was used. The data was initially de-noised and corrected by applying the MRtrix dwidenoise function (21) and Gibbs ringing correction (22). The resulting images were visually controlled, and the volumes with low quality were discarded. The 'Eddy current correction' was subsequently applied (23).

In the context of neuroproprioceptive PT, we did not expect changes in a particular area; hence we analyzed FA across the white matter using a global changes of FA as well as FA changes in 48 white matter regions.

FA global change and changes in 48 regions of interest

A diffusion tensor was fitted to each voxel of the brain, and a fractional anisotropy (FA) map was created for each subject (24). The images were further analyzed using tract-based spatial statistics (TBSS) (25). The TBSS routine consisted of three steps: 1) non-linear registration of all FA images to a chosen template – we chose the FMRIB58_FA standard-space image as a target; 2) application of the non-linear registration identified in the first step, affine registration of each subject to MNI152 space and skeletonization of the mean image; 3) thresholding of the mean skeleton (we used 0.3 as a threshold) and a projection of individual subjects FA maps onto the mean skeleton. Primarily, the (global) mean of the projected FA values over the whole skeleton were compared among subjects.

The resulting skeletonized images were parcellated using the ICBM-DTI-81 white- (26) matter labels atlas consisting of 48 regions, and the mean FA value for each region was computed (regions are listed in Table 3).

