1.6. Statistical analysis

The resulting dataset was further analyzed using the non-parametric Wilcoxon test for assessing the difference between visits. Differences between the treatment groups were identified using the Kruskal-Wallis test. All statistical analyses were performed using Matlab (MATLAB version R2018b). Note that the region-wise analysis was considered exploratory so that there was used an uncorrected significance threshold of 0.05 to select the strongest effects for description. Due to the multiple undertaken tests, many of the presented localized effect results can constitute false positive findings, and thus the observed effects serve rather as initial findings calling for independent validation in a follow-up study. The conservative Bonferroni-corrected threshold across 48 regions would correspond to $0.05/48 \approx 0.0001$, which was not reached by any single one of the effects. However, this is to be expected, as the study sample size was not designed for confirmatory testing of such a large set of hypotheses, but rather for global effect testing. This additional exploratory analysis is intended to provide the reader with further information on the presence/absence and spatial distribution of any potential localized effects outside the global hypotheses testing.

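### Arms were filled by therapist and device availability, not at random, yet the only between-arm test makes no adjustment for the baseline factors collected

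*Combined protocol and SAP*

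**What the plan says.** On allocation, section 1.1 states: "MS patients were divided into three groups by an independent study coordinator according to availability of each therapist (in Groups 1 and 2"). For the stimulation arm the criterion was the "amount of FES devices to borrow (in Group 3"). Randomisation is not mentioned anywhere in the document. Section 1.3 places Group 1 at one hospital ("Therapy was realized at Faculty Hospital Royal Vineyard") and Group 2 at another ("Therapy was realized at Motol University Hospital").

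On analysis, section 1.6 gives one between-arm method: "Differences between the treatment groups were identified using the Kruskal-Wallis test". The only other test is the within-patient Wilcoxon test between visits. No regression, stratification, matching or rule for baseline imbalance is described. Section 1.6 does not name the quantity compared between arms. For FA, section 1.5 makes change the natural reading ("FA global change and changes in 48 regions of interest").

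On covariates, section 1.4 records demographic and disease data, "namely gender, age, length of disease, type of MS (relapsing-remitting, primary or secondary progressive) and EDSS". For baseline comparability, section 1.2 refers the reader to a table ("for their baseline characteristics see Table 1"), which is not in the supplied text.

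**The concern.** When arms are filled by logistics, nothing makes them comparable in expectation. Therapist slots and device stock can follow calendar time, referral route or hospital, and so patient type. Entry is broad: EDSS up to 7.5 with no stated lower limit, and relapsing-remitting as well as progressive disease.

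If the arms differ on a factor that is related to change over the two months, an unadjusted comparison credits the therapy with that factor's effect. Using change scores removes additive baseline differences in the outcome. It does not remove differences in response linked to EDSS, MS type, age or disease duration. The caution in section 1.6 concerns false positives across many regional tests and does not mention confounding. A reader therefore cannot tell whether a reported arm difference would survive adjustment.

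**Working it through.** **The plan's own figure.** Section 1.2 gives 80% power at d = 0.36 with 61 participants. A two-sided paired comparison pooled over arms reproduces it: (1.960 + 0.842)/√61 = 2.802/7.810 = 0.359. The stated power therefore describes the pooled before-after test, not the arm contrasts. With an assumed equal split (61/3 ≈ 20.3 per arm), the pairwise detectable effect is 2.802 × √(2/20.33) = 0.88.

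**Inputs for the bias check.** From the documents: N = 61, three arms, alpha 0.05. Assumed, because the documents give no values: arms 20/20/21, one baseline factor Z shifted in one arm by g SD, correlation ρ between Z and change, and no treatment effect.

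**Bias.** With change = ρZ + √(1 − ρ²) × noise, the expected unadjusted difference between the shifted arm and another arm is ρ × g, in SD of change. It runs from 0.1 × 0.2 = 0.02 to 0.5 × 0.8 = 0.40.

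**Kruskal-Wallis rejection rate on change, nominal 5%** (10,000 replicates per cell, Monte Carlo error about 0.2 points at 5%):

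| ρ | g = 0 | 0.2 | 0.3 | 0.5 | 0.8 |
|---|---|---|---|---|---|
| 0.1 | 4.7% | 4.9% | 4.7% | 5.0% | 5.2% |
| 0.2 | 4.2% | 4.9% | 5.5% | 5.6% | 7.4% |
| 0.3 | 5.0% | 4.7% | 5.7% | 6.9% | 10.1% |
| 0.5 | 4.8% | 5.9% | 7.2% | 10.9% | 21.8% |

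Repeating two cells gave 7.1% (g = 0.5, ρ = 0.3) and 21.7% (g = 0.8, ρ = 0.5). Spreading the imbalance across all three arms, with 0.5 or 1.0 SD end to end, gave 6.8% or 11.6% at ρ = 0.3 and 9.5% or 26.1% at ρ = 0.5.

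**Interval coverage, unadjusted 95% CI.** At ρ = 0.1 it is 94.7% (g = 0.5) and 94.3% (g = 0.8); at ρ = 0.3, 92.3% and 88.1%; at ρ = 0.5, 87.6% and 75.3%. A hand check of the worst cell with 20 versus 20: SE = √(2/20) = 0.316 and bias/SE = 0.40/0.316 = 1.26. Coverage is then about Φ(1.96 − 1.26) − Φ(−1.96 − 1.26) = 0.76, in line with the simulation.

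**Effect of adjustment.** The F test for arm adjusts for Z, two further continuous covariates and three-level MS type.
- Z measured: it rejects in 4.5-5.4% of trials in all 20 cells, and CI coverage is 94.7-95.4%.
- Z measured with reliability 0.7: 4.6-6.2%.
- Z not measured: no protection (21.6% at g = 0.8, ρ = 0.5).

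**Precision cost.** Residual degrees of freedom at N = 61 are 61 − 3 = 58 for arm only. Adding EDSS, age, duration and two MS-type terms gives 58 − 5 = 53, and adding the baseline outcome gives 52. The critical t values are 2.002, 2.006 and 2.007. The ratio of adjusted to unadjusted SE ran from 0.906 (ρ = 0.5, g = 0) to 1.098 (ρ = 0.1, g = 0.8).

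**The case against.** The trial is openly exploratory, its allocation method is disclosed, and its sample size fits the pooled before-after test, which this point does not touch. Arm contrasts with about 20 patients each are imprecise with or without adjustment. Allocation was logistical and run by an independent coordinator, and nothing says patients were placed by prognosis. Across gaps of 0.2-0.5 SD and correlations of 0.1-0.3 the test rejects at 4.7-6.9%, and nothing in the documents supports the extreme cells. Table 1 may already show the gaps. Adjustment cannot separate arm from hospital, so adjusted intervals could reassure falsely, and any model added now is post hoc.

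Much of this stands. The impact is conditional and may be negligible, the pooled result is safe, and adjustment is only a partial remedy. It does not remove the point. Section 1.6 still tests differences between treatment groups. Disclosing the allocation does not show whether a difference survives adjustment, and a baseline table can show gaps but not how far they move a contrast. The limits of adjustment are a reason to state the limitation explicitly beside the model. A fuller protocol is said to be held by the ethics committee, so this reading covers the supplied text only.

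**Conclusion.** The concern holds and should be fixed. Allocation by availability, a single unadjusted between-arm test, and collected but unused prognostic covariates are all plain in the text, and nothing there warns of confounded arm contrasts.

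The size of the problem depends on inputs that the documents do not give. It is negligible for small gaps or weak correlations, and material for large ones, up to about a fifth of null trials declared significant at gap 0.8 SD and correlation 0.5. These figures rest on assumed arm sizes, a single shifted factor and a linear relation with change. Whether the arms were in fact imbalanced cannot be judged here. The problem is confined to the between-arm results.

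**What to change.** 1. State in section 1.6 that the between-arm quantity is change from baseline, and keep Kruskal-Wallis on change as the unadjusted analysis.
2. For global FA, BBS, TUG, MSWS-12 and MSIS-29, add one linear model of change on arm, EDSS, MS type, age and disease duration. Report adjusted arm differences with 95% CIs. Gender is also collected and could be added for one more degree of freedom.
3. Fit one sensitivity version that adds the baseline outcome value, and say so if the two versions disagree.
4. Do not extend the model to the 48 regions.
5. Label the model as added after the fact if it is fitted after the data were seen. Section 1.6 already reports results, so this is likely.
6. State that arm differences are non-randomised associations, and that Group 1 versus Group 2 cannot be separated from hospital or therapist.

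The cost is wording plus five models and five sensitivity versions on data already collected. In the simulation the SE of an arm difference changed by between −9% and +10%; the loss would be larger if several covariates differ by arm. The degrees of freedom above use N = 61. The number analysed for the clinical outcomes is not stated, and a larger number would lower the cost. The remaining downsides are linear-model assumptions that the rank test avoids, and confounding by unmeasured factors, hospital or therapist that no adjustment here can remove.

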Group 3 underwent FES in PCP (16), a method developed at our workplace. Participants first underwent individual two-hour session consisting of postural correction using MPAT and the device (The WalkAide® System, Innovative Neurotronics Inc., [name]) programming. Patients received the device to be used use as much as they felt able to during their normal daily activities.. After fourteen days, the patients received the second individual two-hour session. The patients then continued to use the device daily for the next six weeks.

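### Patients were assigned by free therapist time and loan devices, with no random or concealed step, so the between-group p-values can only be descriptive

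*Combined protocol and SAP*

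**What the plan says.** Section 1.1 describes the trial as multi-arm, parallel-group and exploratory. It never calls it randomised. Assignment follows capacity, that of therapists for the first two groups and that of loan stimulators for the third: "divided into three groups by an independent study coordinator according to availability of each therapist (in Groups 1 and 2) and amount of FES devices". No random sequence, concealment, stratification or minimisation is described anywhere in the text.

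The only blinding stated is that "a blinded assessor evaluated clinical outcomes". Under section 1.3, Groups 1 and 2 received different hands-on methods at two different hospitals, and Group 3 used a wearable stimulator at home. Patients and therapists could therefore not be unaware of the arm.

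Section 1.6 compares the groups with a Kruskal-Wallis test and the visits with a Wilcoxon test, with no covariates. Its warning about false positives is attached to the tests of the 48 white-matter regions. The global analysis is presented as what the sample was sized for.

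**The concern.** A rule based on capacity can be foreseen. If one arm is open, the next assignment is certain. If several are open, the text does not say how the coordinator chose among them. Calling the coordinator independent describes the person and adds no unpredictability to the mechanism.

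A foreseeable assignment lets whoever refers, enrols or books a patient take account of that patient's traits, for example by timing entry. Motivation, ability to travel to a given hospital and willingness to wear a device could matter here, and section 1.4 records none of them. Two of the three methods came from the investigators' own group (section 1.3), a setting in which concealment is worth having.

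At stake is the between-group contrast. The Kruskal-Wallis null distribution assumes that, without a therapy effect, patients are exchangeable between groups. If they are not, a significant group difference in global FA change or in a clinical outcome may reflect who was placed where. A blinded assessor protects the measurement, but the problem lies in the assignment.

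**Working it through.** **1. The plan's own figure.** Section 1.2 states that 61 participants give 80% power at p < 0.05 for d = 0.36. A two-sided one-sample (paired) calculation gives (1.960 + 0.842)/√61 = 2.802/7.810 = 0.359, which matches. The stated figure is therefore a pooled before-after effect on all 61. The group sizes are in a figure that is not shown. Assuming 20 per group, the detectable difference between two groups is 2.802 × √(2/20) = 0.89 SD.

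**2. What foreseeable allocation could do to the Kruskal-Wallis test.** The documents give neither the share of patients steered (s) nor the correlation (r) between the steering trait and the change score. Both are assumptions.

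Model: N = 61; trait z ~ N(0,1); change y = r·z + √(1 − r²)·e with e ~ N(0,1); three roughly equal arms formed at random; no therapy effect. Each patient is then, with probability s, subject to placement by z. The test is Kruskal-Wallis at 0.05.

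The steering pattern matters as much as s and r. At s = 50%:

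| Steering pattern | r = 0.3 | r = 0.5 |
|---|---|---|
| Ordered: lowest, middle and highest third of z each sent to their own arm | 12–14% | 29–31% |
| Highest third sent to one arm, other steered patients kept out of it | 10% | 22% |
| Highest third sent to one arm, everyone else left as they were | 7% | 11% |

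The ranges in the first row reflect simulation error across repeated runs. Under the ordered pattern, other shares give:

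- s = 0: 4–5%.
- s = 10%: about 5% for r from 0.1 to 0.5.
- s = 25%: about 6–7% (r = 0.3) and 10–11% (r = 0.5).
- s = 75%: about 24–25% (r = 0.3) and 63–64% (r = 0.5).

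**3. A second model as a check.** Take arms of 20, 20 and 21 with normal outcomes and no therapy effect, and let selection shift the expected change in one arm by b SD. The rejection rates are 5.0% (b = 0), 8.8% (0.2), 13.9% (0.3), 31.7% (0.5) and 70.3% (0.8). The documents do not determine b either.

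**4. What is not affected.** The Wilcoxon test between visits, pooled over all 61, uses each patient as their own control and ignores group. Its validity as a before-after test does not depend on the allocation rule.

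**The case against.** The strongest reply is that foreseeable is not the same as steered. When only one arm is open, the coordinator has no choice. Selection then needs someone who knows both the capacity and the patient's traits and who times or refuses entry. If capacity fluctuates for reasons unrelated to prognosis, assignment is close to haphazard. The coordinator's independence also lowers the risk of deliberate steering. All of this stands, and it is why the point is confined to what the rule fails to secure.

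A reader might infer evidence of steering from section 1.3, where it says "The therapists offered their full help and adopted the schedule, so each patient was able to complete the whole program". That sentence is about completing the programme once assigned; it does not say that slots were opened or closed for incoming patients. Likewise "Patients received the device to be used use as much as they felt able to during their normal daily activities" describes use of the device after allocation. That the coordinator knew the patient before assigning, or that assignment preceded baseline assessment, is also not stated.

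A reader might also conclude that adjustment could not help at all. That is too strong. EDSS, MS type and disease duration are recorded, and baseline BBS, TUG and MSWS-12 partly stand in for expected walking gain. Adjustment could remove part of any imbalance, though not what is due to motivation or travel. The plan in section 1.6 adjusts for none of these.

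Finally, the trial is labelled exploratory and discloses its rule. That limits the seriousness but does not settle the matter: section 1.6 sets the exploratory regional tests apart from the global hypothesis testing and says nothing about allocation, so the other between-group results carry no warning.

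**Conclusion.** The point holds for the between-group comparison. The written rule contains no chance element and no concealment, and the unadjusted Kruskal-Wallis test relies on an exchangeability that the rule does not provide. Steering is possible but not shown.

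Its effect on false positives cannot be fixed from the documents. It is near the nominal 5% if 10% of patients were steered. It is about 7% to 31% if half were, depending on the steering pattern and on r between 0.3 and 0.5.

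Two stronger conclusions are not supported. First, a spurious group difference should not be set against d = 0.36, which is the pooled paired figure. The corresponding value between two groups of 20 is about 0.89. Second, the pooled before-after result is not undermined by how the groups were formed, although without an untreated group it has its own limits.

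The conclusion assumes that section 1.1 gives the complete rule. Section 1.2 says that a full protocol is held by the ethics committee, and its content cannot be checked here.

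**What to change.** **For this trial.** Section 1.1 places it in the past ("The Multi-Arm Parallel-Group Exploratory Trial (NCT04355663) was realized between May 2015 and May 2017"), so the allocation can no longer be changed. State in sections 1.1 and 1.6 that allocation was neither random nor concealed. Report all between-group p-values, including those for global FA and the clinical outcomes, as descriptive and subject to selection bias, not as evidence that one therapy differs from another. The cost is a few sentences and a more cautious reading of the group contrast.

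**As a design rule, at planning or in the follow-up study that section 1.6 calls for.** Keep the capacity limits. For each patient, log which arms have a free slot or device, then draw the arm from a concealed computer list among those open arms only. Store the open set with the patient, and compare arms within strata of that set, for example with a van Elteren or a stratified permutation version of the rank test. Patients with only one open arm stay in the before-after analysis but leave the between-arm contrast. The downside is therefore some lost precision in that contrast; the limits on therapists and devices stay as they are.
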